9.5.3 Geometric Mean Concentration (GMC)

The GMC will be calculated as the anti-logarithm of \sum (log transformed concentration/n), i.e. as the anti-logarithm transformation of the mean of the log-transformed concentration, where n is the number of subjects with concentration information in the relevant group. The geometric standard deviation (GSD) will be calculated as the anti-logarithm transformation of the standard deviation of the log-transformed concentration. The 95% confidence interval (CI) for GMC will be calculated as the anti-logarithm transformation of the sample mean of the log-transformed concentrations.

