## Further details on efficacy analyses will be provided in the SAP.

## 13.1.4 Immunogenicity Analysis

Immunogenicity results will be summarized using descriptive statistics including 95% CIs for all available assays at all relevant time points. These summaries will be provided for the FAS and PPS-I.

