9.5.4 Fold Rise in Antibody Concentrations

Fold rise in antibody concentrations is summarized using geometric mean fold rise (GMFR), defined as the geometric mean of the ratio between post vaccination assay result and baseline assay result. The GMFR is calculated as the anti-logarithm of \sum (log transformed (post-vaccination concentration/ pre vaccination concentration)/number of subjects in the relevant group). GSD for the fold rises and 95% CI for the GMFR are calculated in the same manner as for GMC.

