11.6 Secondary Immunogenicity Endpoint

11.6.1 Immunogenicity of HIL-214

The secondary immunogenicity endpoints for the trial are pan-Ig and HGBA blocking antibody concentrations. These endpoints will be summarized as seroresponse rates (see Section **9.5.3**), GMCs and GMFRs (see Section **9.5.4**) for HBGA blocking antibody concentrations and for pan-Ig antibody concentrations collected at Visit 1(Day 1), Visit 2 (28 to 56 days post dose 1 - prior to dose 2) and Visit 3 (28 days post, and when the subjects reach the age of 1 year (Visit 4), 18 months (Visit 5) and 2 years (Visit 6) (see Section **9.2.5**). These estimates will be presented by trial arm separately for GI.1 and GII.4 NoV genotypes. Summaries of results for Visits 1 through Visit 4 will be included in the primary and secondary efficacy analysis. 18 months (Visit 5) and 2 years (Visit 6) results will be summarized at the end of trial.

The number of subjects with seroresponse, seroresponse rate and 95% CI on post-dosing visits will be presented. The two-sided exact 95% CI will be estimated using the Clopper-Pearson exact method (Clopper CJ & Pearson ES, 1934). For details of the derivations of GMC and GMFR, see section 9.5.3. Longitudinal plots and reverse cumulative distribution plots for concentrations will be presented by genotype and trial arm. The secondary immunogenicity analyses will be performed on the FAS and the PPS-I.

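### The SAP's stated 95% CI for the GMC is the GMC point estimate itself, and the GMFR inherits the rule, so neither summary has a defined interval

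*SAP*

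**What the plan says.** SAP 9.5.3 contains three definitions in sequence:

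- The GMC is calculated "as the anti-logarithm transformation of the mean of the log-transformed concentration", with n limited to subjects who have a concentration.
- A spread measure follows: "The geometric standard deviation (GSD) will be calculated as the anti-logarithm transformation of the standard deviation of the log-transformed concentration".
- The interval is then defined: "The 95% confidence interval (CI) for GMC will be calculated as the anti-logarithm transformation of the sample mean of the log-transformed concentrations".

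SAP 9.5.4 carries the rule over: "GSD for the fold rises and 95% CI for the GMFR are calculated in the same manner as for GMC". Its first sentence defines the GMFR as the geometric mean of the post-vaccination to baseline ratio. The formula that follows ends in the divisor "pre vaccination concentration)/number of subjects in the relevant group".

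SAP 11.6.1, which describes the analysis itself, adds no interval method for either summary: "For details of the derivations of GMC and GMFR, see section 9.5.3". The one interval method it names is for the seroresponse rate: "The two-sided exact 95% CI will be estimated using the Clopper-Pearson exact method".

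Protocol 13.1.4 asks for intervals without giving a formula: "Immunogenicity results will be summarized using descriptive statistics including 95% CIs for all" available assays and relevant time points, in the FAS and PPS-I.

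**The concern.** An interval needs two limits, and each limit needs a measure of uncertainty. The sentence in 9.5.3 supplies neither. It repeats the operation that produced the point estimate and does not use the standard deviation introduced one sentence before. Because 9.5.4 and 11.6.1 both lean on 9.5.3, the gap covers every GMC and GMFR, for both assays, both genotypes, each visit and each arm.

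The SAP is where the protocol's request for 95% CIs should become a formula. As it stands, the programmer has to supply the method, including the choice between a t and a normal quantile and the choice of n.

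There is also a smaller inconsistency. The GMC divisor is restricted to subjects with a result, while the GMFR divisor is worded as everyone in the group. The two should match.

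**Working it through.** The documents report no GMC or GMFR value, so there is no figure of the plan's own to reproduce. The check is algebra, followed by a sense of scale.

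**1. The rule as written.** Let L be the log concentration of each subject with a result, n the number of such subjects, and m the mean of L.

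- GMC (SAP 9.5.3) = anti-log(Σ L/n) = anti-log(m).
- Stated 95% CI (SAP 9.5.3) = anti-log(m).
- The two are identical for any data, so the interval factor is 1.00.

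The same holds for the GMFR, with L replaced by the log of the post/baseline ratio.

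**2. Numerical confirmation on simulated log-normal data, n = 1000.** Post-vaccination values were drawn around 1000 with natural-log SD 1.2, and baseline values around 100 with natural-log SD 1.0. These values are illustrative and not taken from the documents.

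| Summary | Point estimate | Stated CI rule | t-based 95% CI on the log scale |
|---|---|---|---|
| GMC | 936.97 | 936.97 | 870.6 to 1008.4 |
| GMFR | 9.116 | 9.116 | 8.29 to 10.03 |

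**3. Width of the usual interval.** The documents give no SD for the log values. Assume a log10 SD of 0.5 to 0.7 and n = 1400 results per arm (1500 per arm are planned, SAP 8.0). The factor by which the GMC is multiplied and divided is 10^(1.96 × SD/√n), with √1400 = 37.42:

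- SD 0.5: 1.96 × 0.5/37.42 = 0.0262, and 10^0.0262 = 1.062.
- SD 0.7: 1.96 × 0.7/37.42 = 0.0367, and 10^0.0367 = 1.088.

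At this n, using t(0.975, n−1) in place of 1.96 does not change the result to two decimals. A wider assumed range, natural-log SD 0.8 to 1.6 with the t quantile, gives factors of 1.04 to 1.08 at n = 1500 and 1.05 to 1.10 at n = 1000.

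**4. Search for a repair elsewhere.** SAP 9.5.4 defers to 9.5.3, SAP 11.6.1 defers to 9.5.3, and Protocol 13.1.4 gives no formula. The exploratory sections are not legible and cannot be checked, but 11.6.1 directs the secondary endpoints to 9.5.3 and not to those sections.

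**The case against.** The best answer is that the intent is plain. The sentence announces a 95% confidence interval directly after the mean and SD of the logs have been defined, and any statistician would read it as the anti-log of the confidence limits of the mean. A zero-width interval would be caught at the first programming check. The remaining ambiguity between t and normal is negligible at the planned arm sizes. All of this stands. It makes the point minor, but it does not put a formula in the SAP. The sentence is grammatically complete, so text lost in conversion is an unlikely explanation.

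It is also fair to say that nothing inferential depends on these intervals. The testing strategy in SAP 11.5.1 covers the primary and key secondary efficacy endpoints only, and Protocol 13.1.4 describes the immunogenicity analysis as descriptive. That stands too.

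A reader might infer more from the GMFR divisor: that a child without a paired sample counts in the denominator with nothing in the sum, in effect as a fold rise of 1, so that missing bloods pull the GMFR toward 1. The similar divisor for the seroresponse rate in 9.5.2 makes that reading possible. The documents do not support it as the plan's meaning. The first sentence of 9.5.4 defines the GMFR as a geometric mean of ratios, and a ratio exists only where both results exist. The substitution rules in 9.5.1 concern values outside the assay limits, and no visible rule fills in a missing result. What remains is loose wording that disagrees with 9.5.3.

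**Conclusion.** The point holds, at low severity. Followed literally, SAP 9.5.3 yields no lower or upper limit for the GMC, and through 9.5.4 none for the GMFR. That conclusion is algebraic and rests on no assumption. The size does rest on assumptions: with a log10 SD of 0.5 to 0.7 and 1400 results per arm, the missing interval is a factor of about 1.06 to 1.09 either side of the estimate, against 1.00 as written.

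It would be wrong to conclude that the immunogenicity endpoints as a whole lack intervals, since the seroresponse rate has a specified exact method. It would also be wrong to conclude that any test, the sample size or the efficacy result is affected.

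**What to change.** Two sentences in the SAP:

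- **9.5.3:** replace the interval sentence with: *95% CI = anti-log of [mean log concentration ± t(0.975, n−1) × SD/√n], where SD is the standard deviation of the log concentrations and n is the number of subjects with a result at that visit.*
- **9.5.4:** apply the same formula to the log fold rises, and change the divisor to: *number of subjects with both a baseline and a post-vaccination result at that visit.* This matches the 9.5.3 denominator and the definition that opens 9.5.4.

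The cross-reference in 11.6.1 can then stay. The cost is an editorial amendment by the route in SAP 6.0, with no new data and no change to any test. If the tables have already been programmed, the clinical study report should state the formula and the n that were used.

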9.5.4 Fold Rise in Antibody Concentrations

Fold rise in antibody concentrations is summarized using geometric mean fold rise (GMFR), defined as the geometric mean of the ratio between post vaccination assay result and baseline assay result. The GMFR is calculated as the anti-logarithm of \sum (log transformed (post-vaccination concentration/ pre vaccination concentration)/number of subjects in the relevant group). GSD for the fold rises and 95% CI for the GMFR are calculated in the same manner as for GMC.

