9.1.2 Full Analysis Set (FAS)

The FAS will include all subjects who are randomized and received at least 1 dose of HIL-214 or placebo. Subjects will be analyzed according to their randomized trial arm.

A subject may be excluded from the FAS due to major Good Clinical Practice violations.

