9.5.2 Seroresponse Rate

Seroresponse is defined as a 4-fold increase from baseline in anti-Nov antibody concentrations as measured by histo-blood group antigen (HBGA) blocking assay and pan-immunoglobulin enzyme-linked immunosorbent assay (pan-Ig), to GI.1 and GII.4 and to both GI.1 and to GII.4. If the baseline value is missing, seroresponse will not be calculated. Subjects without a seroresponse will be referred to as non-responders. The seroresponse rate is defined as the ratio of the number of subjects who met the seroresponse criteria, divided by the number of subjects in the relevant group in the analysis set.

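### The divisor in the SAP 9.5.4 formula for the geometric mean fold rise conflicts with that section's own definition and with SAP 9.5.3; programmed as written, it pulls the estimate toward 1 wherever pairs are missing

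*SAP*

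**What the plan says.** SAP 9.5.4 describes the GMFR twice. In words, it is "defined as the geometric mean of the ratio between post vaccination assay result and baseline assay result". As a calculation, it is the anti-log of the summed log "post-vaccination concentration/ pre vaccination concentration)/number of subjects in the relevant group". The section closes with: "GSD for the fold rises and 95% CI for the GMFR are calculated in the same manner as for GMC".

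SAP 9.5.3, directly before it, averages log concentrations with a restricted n: "where n is the number of subjects with concentration information in the relevant group".

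SAP 11.6.1 cites 9.5.4 when it first lists GMCs and GMFRs, and later says: "For details of the derivations of GMC and GMFR, see section 9.5.3". Section 9.5.3 contains no fold-rise formula.

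On populations, SAP 11.6.1 states: "The secondary immunogenicity analyses will be performed on the FAS and the PPS-I". The FAS does not depend on blood sampling: "The FAS will include all subjects who are randomized and received at least 1 dose of HIL-214 or placebo". The PPS-I (SAP 9.1.5) requires a baseline sample but no post-dose sample. SAP 9.2.5 drops PPS-I results from samples drawn outside the listed windows and does not say that the child leaves the set.

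**The concern.** A post/baseline ratio exists only for a child with both values, so a geometric mean of ratios divides the summed logs by the number of such children. The formula in 9.5.4 divides by the group. A child without a pair adds nothing to the numerator but is counted in the denominator, which is equivalent to assigning that child a fold rise of exactly 1.

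Unpaired children can occur in both analysis sets. In the FAS, either the baseline or the post-dose result may be absent. In the PPS-I the route is a missing or out-of-window post-dose result, since a baseline sample is a condition of entry.

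The GMFR for GI.1 and GII.4 is a named secondary immunogenicity summary. Two programmers could each follow a sentence of 9.5.4 faithfully and report different values from the same data. The point estimate could also be built on a different n from its own interval.

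**Working it through.** The documents state no GMFR value, so there is no figure to reproduce. The check is algebra on the two descriptions in 9.5.4, followed by a range.

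**Inputs from the documents**
- Group size N: about 1500 per arm (SAP 8.0 and 8.2).
- Divisor as written: everyone in the group (SAP 9.5.4).
- Divisor implied by the verbal definition: n, the children with both results at the visit.

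**Assumptions, because the documents are silent**
- Share without a pair, m = 1 − n/N: 5% to 30%.
- Paired GMFR: 0.7 to 20, for illustration.
- SD of the natural-log fold rise: 1, used only for the interval.

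**Formulas.** Let S be the sum of log ratios over the n paired children.
- By definition: G = exp(S/n).
- As written: exp(S/N) = exp((S/n) × (n/N)) = G^(n/N) = G^(1 − m).

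**Worked case.** N = 1500, m = 10%, so n = 1350. With G = 10, S = 1350 × 2.3026 = 3108.5. By definition, exp(3108.5/1350) = 10.0. As written, exp(3108.5/1500) = exp(2.0723) = 7.94.

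**Range: value the literal formula would report**

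| Paired GMFR | m = 5% | m = 10% | m = 20% | m = 30% |
|---|---|---|---|---|
| 20 | 17.22 | 14.82 | 10.99 | 8.14 |
| 10 | 8.91 | 7.94 | 6.31 | 5.01 |
| 4 | 3.73 | 3.48 | 3.03 | 2.64 |
| 2 | 1.93 | 1.87 | 1.74 | 1.62 |
| 1 | 1.00 | 1.00 | 1.00 | 1.00 |
| 0.7 | 0.71 | 0.73 | 0.75 | 0.78 |

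The pull is toward 1 from either side. A single unpaired child in 1500 moves 10 only to 10^(1499/1500) = 9.985.

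**Consistency with the interval.** Suppose the CI is built in the GMC manner, on the n with data. With G = 10, log SD 1 and n = 1350, the half-width on the log scale is 1.96/√1350 = 0.0533. The 95% CI is 10 × exp(±0.0533), or 9.48 to 10.55. The literal point estimate at the same m is 7.94, which lies outside that interval.

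**After the fix.** Dividing by n returns G at every m, so 10.0 stays 10.0.

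**The case against.** The strongest reply is that the SAP, read as a whole, already points to paired data. The first sentence of 9.5.4 defines a geometric mean of ratios. The GSD and CI follow the GMC, whose n is restricted to subjects with data. SAP 11.6.1 refers to 9.5.3 for the derivation of both statistics, and SAP 11.0 summarises continuous variables with the number of observations. No sentence says that a missing pair counts as no change. The mismatch between point estimate and interval is itself a sign that the literal reading was not intended.

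Much of this stands: the paired divisor is probably what the authors meant. It does not remove the conflict, for three reasons.
- The only explicit fold-rise formula is the one with the unrestricted divisor.
- SAP 9.5.3 treats the group as wider than the subjects with data, and SAP 9.5.2 uses a similar unqualified denominator for seroresponse ("divided by the number of subjects in the relevant group in the analysis set"). The phrase in 9.5.4 therefore cannot safely be read as meaning paired children only.
- The references in 11.6.1 disagree with each other, citing 9.5.4 in one place and 9.5.3 in another.

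A reader might infer more than this, and the documents do not support it:
- **That every missing sample biases the GMFR.** The effect is per unpaired child per visit. A missing post-dose sample matters only at its own visit, and a second missing sample in a child already unpaired at that visit adds nothing.
- **That the GMFR is always understated.** A value of 1 does not move, and a value below 1 moves up.
- **That the plan expects 20% to 30% missing pairs.** That range in SAP 8.1 is an allowance for drop-out and non-evaluable samples when planning efficacy cases. It is not a serology rate.
- **That the result would be taken for waning.** This would need m to rise over visits, which the documents do not quantify. GMCs with a restricted n and longitudinal plots of the same assays are also reported and would help expose an artefact.

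**Conclusion.** The point holds as an internal inconsistency. The formula in SAP 9.5.4 contradicts the definition in the same section and the available-data n in 9.5.3, and no other passage clearly overrides it. It would be too strong to say that the SAP has settled on an all-subjects divisor or that the reported GMFR will be biased; bias arises only if the formula is programmed as written.

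In that case the error follows exactly from the share of missing pairs. Under the assumed 5% to 30%, a paired GMFR of 10 is reported as 8.9 to 5.0. Both the missing share and the fold rise are assumptions, and the shrinkage is measured against the paired estimate, not against what complete data would have shown. The interval comparison rests further on an assumed log SD of 1.

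The GMFR is a descriptive secondary summary with no success criterion. The primary and key secondary efficacy tests do not use it. The correction is nonetheless worth making, because the SAP should yield one number for a named secondary summary.

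**What to change.** In SAP 9.5.4, replace the divisor with the number of subjects in that arm and analysis set who have both a baseline and a post-vaccination result at the visit in question. State that the same n is used for the GSD and the 95% CI, and show it in the table beside each GMFR. In SAP 11.6.1, point the GMFR derivation to 9.5.4 and the GMC derivation to 9.5.3.

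The cost is one phrase in 9.5.4, one corrected cross-reference and one n column in the tables. No new data are needed, and the design, analysis sets and efficacy analyses are unchanged.

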10.0 Interim Analyses

A formal interim analysis (interim evaluation of the trial objectives) is not planned for this study.

11.0 Statistical Methods

All statistical analyses will be performed using SAS® Version 9.4 or higher.

Unless otherwise noted, continuous variables will be summarized using the number of observations (n), mean, standard deviation, median, first quartile (Q1), third quartile (Q3), minimum, and maximum values. The minimum and maximum values will be displayed to the same level of precision as the raw data; the mean, median, Q1 and Q3 values to one additional decimal place and the standard deviation to two additional decimal places.

Categorical variables will be summarized using counts and percentages. Percentages will be rounded to one decimal place, except 100% will be displayed without any decimal places, and percentages will not be displayed for zero counts.

Listings will be provided for relevant summaries.

11.1 Subject Disposition

The number and percentage of subjects screened and who failed screening and the reason for failure, and the number and percentage of subjects randomized and not randomized and the reason for not being randomized will be summarized. Number and percentage of subjects randomized by country and site, as well as the number of subjects included in each analysis set will be summarized overall and by trial arm. For the FAS, mFAS, the trial group will be the randomized trial arm. For all other analysis sets, trial arm will be that actually received by the subject.

The number and percentage of randomized subjects will be summarized by visit completed and randomized trial arm and overall. Number and percentages of subjects who discontinued the vaccination regimen as well as those who discontinued the study, along with the reasons for discontinuation by last visit completed will be reported.

11.2 Demographic and Baseline Characteristics

Subject demographics and baseline characteristics will be summarized descriptively by trial arm in the SAF, FAS, mFAS, PPS-E, and PPS-I. Demographic information to be obtained in CRF will include date of birth, sex, race, and ethnicity as described by the subject's LAR. Country and age (months) at randomization will also be summarized (see Section 9.2.3). Weight, length, and head circumference at baseline will be summarized.

Medical History will be coded using the Medical Dictionary for Regulatory Activities (MedDRA) version 24.1 and will be summarized by preferred term (PT) and primary system organ class (SOC) for the SAF. MedDRA version will not be updated during the study.

11.3 Vaccine/Investigational Product

11.3.1 Extent of Exposure

Number and percentage of subjects receiving only one dose or both doses of trial vaccine will be presented by trial arm in the SAF. Time between trial doses in days will also be summarized by trial arm in the SAF. A listing of the vaccine administration will be provided.

11.3.2 Prior and Concomitant Medications and Vaccines

Prior and concomitant medications and vaccines (see Section **9.2.2**) will be summarized by preferred drug name according to World Health Organization Drug Dictionary (WHO-DD) (GLOBAL B3Sep21). Prior and concomitant medications will be summarized separately for the SAF. The number and percentage of subjects administered prior medications, concomitant medications, and vaccines, in each trial arm will be summarized by system organ class and preferred term in the SAF. A by-subject listing of all prior and concomitant medications, and vaccines will be provided.

11.4 Important Protocol Deviations

The number and percentage of subjects with important protocol deviations as described in the protocol deviations guidance and medically reviewed will be summarized overall, by deviation category and by trial arm in the FAS. A listing by-subject listing of important protocol deviations will also be provided.

The categories of important protocol deviations, which may affect evaluation of efficacy or immunogenicity, include:

- 1. Not meeting selected entry criteria;
- 2. Receiving wrong or incomplete trial product;
- Receiving prohibited therapies (e.g., antipyretics and/or analgesic medications administered within 24 hours prior to investigational vaccine or placebo, non-live and orally administered live vaccines within 14 days of investigational vaccine or placebo, parenterally administered live vaccine within 28 days of investigation vaccine or placebo);
- 4. Protocol-described regimen not followed for storage of investigational vaccine or placebo;
- 5. Vaccination regimen described in protocol not followed for administration of investigation vaccine or placebo (e.g., administered out of window, or in incorrect injection site);
- 6. Other important protocol deviations that may affect efficacy evaluation;
- 7. Other important protocol deviations that may affect immunogenicity evaluation.

Subjects with these deviations will be excluded from PPS-E and/or PPS-I, as appropriate.

The number and percentage of subjects with important protocol deviations, which led to the exclusions of subjects from PPS-E and PPS-I, will be summarized overall, by deviation category and by trial arm, in the FAS and mFAS, respectively.

All protocol deviations are recorded in a system of record, and a subset of those are defined as Important protocol deviations.

The study team and the HilleVax team will conduct periodic blinded reviews of the deviation data from the electronic system of records during the study conduct, and the resulting set of evaluable subjects.

Exclusions from the per protocol sets will be determined programmatically and via medical review of relevant blinded listings prior to the unblinding of the subject's trial vaccine assignments for the primary analyses. The PPS-E and PPS-I will not be revised for the end-of-trial analyses.

